RESEARCH PROTOCOL

Date	3/1/17
Title	Impact of diet on functional gastrointestinal symptoms; a national population based survey
Principal Investigator	[name]
Sub-Investigators	[name]
Research Specialist	[name], MS
Department	Department of OB/Gyn, Division of Urogynecology and Reconstructive Pelvic Surgery; TriHealth Digestive Institute, Division of Gastroenterology
Hatton #	17-006

Purpose of Study:

- To delineate the role of diet in functional gastrointestinal (GI) symptoms.
- To determine the prevalence of functional GI disorders in the general population.
 - **Primary Aim:** To describe common triggers for food-related GI symptoms.
 - **Secondary Aims:** To assess prevalence of self-reported functional GI disorders and awareness of dietary modification programs for GI symptoms.

Hypothesis or Research Question

- We hypothesize that functional GI symptoms are very common, and may not be associated with formal diagnoses.
- We further hypothesize that certain foods may be triggers for symptoms, and that food ‘sensitivity’ is common in the population.
- Finally, we hypothesize that the majority of people are aware of gluten-free eating but are less aware of other dietary treatments for GI symptoms.

Background

Hippocrates said “Let food be thy medicine, and medicine be thy food”¹. This quote rings true today, more than ever before. Functional GI disorders, involving symptoms such as gas/bloating, diarrhea, constipation and abdominal pain, are estimated to impact between 35 and 45 million Americans, an overwhelming 15-20% of the population. These symptoms are responsible for upwards of 20 billion dollars in healthcare costs and extensive loss of quality of life for sufferers^{2,3}. Moreover, many patients suffer in silence, with 67% of subjects waiting more than a year before treatment, and 11% waiting over 10 years⁴. Irritable bowel syndrome or IBS is the most prevalent functional GI disorder⁵, and several recent studies support the idea that dietary modifications may be key to alleviating this condition⁶⁻¹⁶.

Food sensitivities and reported intolerance to lactose, gluten, wheat, and carbohydrates are increasing globally. While the mechanism is unclear, restriction of particular foods or food groups may alleviate functional GI symptoms. Indeed, both gluten-free and low-FODMAP diets

have been shown to reduce symptoms in affected patients, and not exclusively in those with celiac disease or lactose intolerance^{16,17}.

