 - Demographic data will be described using frequency (percentage) for categorical variables and mean (standard deviation) or median (interquartile range) for continuous variables.
 - Categorical data will be analyzed using Pearson's chi-square or Fisher's exact test; continuous data will be analyzed using Student's t-test.
 - A goal of greater than 500 subjects is sought. Sufficient emails will be obtained from SurveyMonkey® to accomplish this sample size.

Ethical Considerations

- **Informed consent**
 - By completing the survey, providers will be giving their consent to participate. No separate informed consent will be administered.
- **Privacy information**
 - The surveys are completely confidential. No identifying information will be obtained.

Cost/Budget

- Approximately \$3500 for the use of the email addresses.

Estimated Period of Time to Complete Study	
When will study begin?	2/1/2017
Protocol Development Completed	2 weeks
Admin Review Time	2 weeks
IRB Approval	3 weeks
Data collection	8 weeks
Data analysis	4 weeks
Presentation development (if applicable)	N/A
Manuscript Development (if applicable)	4 weeks
Journal submission process (if applicable)	6 months
Study closure	2 months

References

1. Chey WD. Food: The Main Course to Wellness and Illness in Patients With Irritable Bowel Syndrome. *The American journal of gastroenterology*. 2016.
4. Association AG. IBS in America Survey. 2015.
5. Saha L. Irritable bowel syndrome: pathogenesis, diagnosis, treatment, and evidence-based medicine. *World journal of gastroenterology : WJG*. 2014;20(22):6759-6773.
6. Wong WM. Restriction of FODMAP in the management of bloating in irritable bowel syndrome. *Singapore medical journal*. 2016;57(9):476-484.

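### Does the plan need Welch's t-test and an age- and sex-adjusted odds ratio in place of Student's t-test and crude tables alone?

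*Combined protocol and SAP*

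**What the plan says.** All references are to the combined protocol and SAP.

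- **Statistical Analysis**, tests: "Categorical data will be analyzed using Pearson's chi-square or Fisher's exact test; continuous data will be analyzed using Student's t-test". No groups, outcome or significance level are attached to these tests, and no regression or adjusted estimate is mentioned.
- **Statistical Analysis**, demographics: "Demographic data will be described using frequency (percentage) for categorical variables", with "mean (standard deviation) or median (interquartile range) for continuous variables". The only continuous variables the text refers to are therefore demographic. The sample size goal is more than 500.
- **Purpose of Study**: the primary aim is "To describe common triggers for food-related GI symptoms". The secondary aims are "To assess prevalence of self-reported functional GI disorders and awareness of dietary modification programs for GI symptoms". A broader purpose stands above them: "To delineate the role of diet in functional gastrointestinal (GI) symptoms".
- **Hypothesis or Research Question**: "We hypothesize that functional GI symptoms are very common, and may not be associated with formal diagnoses".
- **Background**: functional GI disorders affect "an overwhelming 15-20% of the population". This is background information, not a design assumption.
- **Participants** and **Data Collection**: men and women aged 18 to 80. Demographic items are collected but not listed in the text; the survey instrument is described as attached and is not part of the text supplied.

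**The concern.** Chi-square, Fisher and t-tests are usually used to compare groups, and the descriptive aims need only proportions. A reader may therefore infer that some groups will be compared. Respondents with and without symptoms are the natural pair, given the stated purpose about the role of diet.

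Two weaknesses would follow from such a comparison. First, Student's t pools the variances, so it is mis-sized when group sizes and standard deviations both differ. A symptomatic share of 15-20% would make the groups very unequal. Second, nothing is randomised. If age or sex is related both to symptoms and to the answer being compared, a crude table shows an association that does not exist within age and sex groups. At stake would be false claims that diet plays a role. The remedies, Welch's t and one logistic model, look almost free.

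**Working it through.** **1. Is the comparison in the plan?** The three aims are to describe triggers, estimate prevalence and estimate awareness. Each is a proportion in the whole sample or within sufferers. No section sets symptomatic against asymptomatic respondents. The goal of more than 500 comes with no calculation to reproduce. What it gives these aims is precision, with half-width 1.96 × √(p(1−p)/500):

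- p = 15%: 3.1 points
- p = 20%: 3.5 points
- p = 50%: 4.4 points

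Neither the choice of t-test nor an adjusted odds ratio enters this formula.

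**2. Size of Student's t if the comparison were made.** Assumptions: n = 500, two-sided 0.05, groups n₁ (symptomatic) and n₂, SD ratio r (symptomatic to other). The documents give none of the splits or ratios.

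- Pooled variance: s² = [(n₁−1)r² + (n₂−1)]/498
- Variance the test uses: A = s²(1/n₁ + 1/n₂)
- True variance: T = r²/n₁ + 1/n₂
- True size ≈ 2 × [1 − Φ(1.965 × √(A/T))]

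For 75 against 425 (15% of 500) with r = 1.5: s² = (74 × 2.25 + 424)/498 = 1.186, A = 0.01860, T = 0.03235, √(A/T) = 0.758, size 0.136. The same formula gives:

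| Split | r = 0.8 | r = 0.9 | r = 1.1 | r = 1.5 |
|---|---|---|---|---|
| 75 / 425 | 0.022 | 0.034 | 0.066 | 0.136 |
| 200 / 300 | 0.040 | 0.045 | 0.054 | 0.069 |
| 250 / 250 | 0.049 | 0.049 | 0.049 | 0.049 |

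Simulation agrees (0.134 to 0.135 for 75/425 at r = 1.5), and Welch's t stays at 0.048 to 0.052. The error needs both unequal groups and clearly unequal SDs. The variable most likely to be tested is age, which is bounded at 18 to 80. Simulating a variable with those bounds, at SD ratios 0.8 to 1.1, gives Student sizes of 0.025 to 0.067 over the splits 75/425, 100/400 and 200/300. A slightly mis-sized test on a demographic variable changes no aim.

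**3. Size of confounding by sex if the comparison were made.** Assumptions: half the sample are women, and symptoms and food sensitivity are unrelated within each sex.

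*Mild case*: symptoms 17% in women and 13% in men, sensitivity 25% and 20%. Expected counts in 500:

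- symptomatic: 17.125 sensitive, 57.875 not
- others: 95.375 sensitive, 329.625 not

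Crude odds ratio = (17.125 × 329.625)/(57.875 × 95.375) = 1.02. The standard error of its log is 0.299, so the shift is ln(1.0226)/0.299 = 0.075. The false rejection rate is Φ(−1.96 + 0.075) + Φ(−1.96 − 0.075) = 5.1% (simulated: 5.2%).

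*Strong case*: symptoms 20% and 10%, sensitivity 40% and 20%. Counts are 25, 50, 125 and 300. Odds ratio = (25 × 300)/(50 × 125) = 1.20, standard error 0.267, shift 0.683, rate 10.5% (simulated: 11.1%). With a 40% symptomatic share (50% and 30%), the odds ratio is 1.22 and the rate 16.9% (simulated: 17.2%).

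If sex is related to only one of the two variables, the simulated rate is 5.0 to 5.2%.

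**4. Confounding by age.** Simulated false rejection rates when age acts in the same direction on both variables, with the implied odds multiplier from 18 to 80 (6.2 decades):

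| Odds ratio per decade | Multiplier | 15% share | 40% share |
|---|---|---|---|
| 1.1 | 1.1^6.2 = 1.8 | 5.3% | 5.2% |
| 1.2 | 1.2^6.2 = 3.1 | 6.7% | 7.8% |
| 1.35 | 1.35^6.2 = 6.4 | 15.7% | 23.1% |

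The large rates need a 6.4-fold change in the odds of both variables over the age range. The documents report no age or sex association of any size.

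**5. Would adjustment serve its purpose?** Only partly. Food sensitivity may be reported because food provokes symptoms, and diets are often adopted because of symptoms. Independence of symptoms and sensitivity given age and sex is therefore not a natural null hypothesis, and adjusting for age and sex does not address the direction of the relation.

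**The case for a change.** The strongest case for the concern is that tests are planned which the aims do not need, so some comparison is probably intended, and the purpose about diet makes symptom groups the likely choice. The changes are cheap: at 75 against 425 with equal SDs and a 0.35 SD difference, Welch has 79.0% power against 79.6%. Adjustment lowers 80% power to 79.8% without confounding and to 75.5% in the strongest age case. Fixing the method in advance would also prevent a choice between crude and adjusted results after the data are seen.

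The arithmetic behind this stands, and so does the observation that the tests are tied to no named groups, outcome or significance level. That is a lack of detail about what will be tested, and changing the t-test or adding a model does not resolve it. The rest is inference about an intention the plan does not state. For a descriptive question, such as whether sufferers know more about diets, the crude table is the right answer. The adjusted odds ratio would be a supplement for a causal reading that the aims do not make, and it needs age and sex items that the text does not confirm.

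**Conclusion.** The concern does not hold. Followed as written, the plan gives sound trigger, prevalence and awareness estimates under either t-test and with or without an adjusted model. The possible harm depends on an unstated comparison and on assumed inputs. Student's t is at its nominal level with equal groups or equal SDs, and crude tables are close to 5% under mild confounding. The striking figures (0.136 for the t-test, 15.7 to 23.1% for crude tables) require an SD ratio of 1.5 in a 75/425 split, or a 6.4-fold age effect on both variables.

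This rests on reading the aims as descriptive, which is how they are worded, and on the text alone. The survey instrument could contain continuous scores that are not visible here. Welch's t and an adjusted odds ratio are reasonable preferences; their absence is not an error. Which groups and outcomes the tests compare is a fair question to the sponsor, but a different point.
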